#### *Data Storage and Transmission*

A VA intranet SharePoint site will be used to facilitate coordination across the multiple study sites. The SharePoint site will be used, in part, to store consent forms. Informed consent forms, HIPAA Authorization forms, and HIPAA supplement forms will be securely faxed and uploaded to SharePoint for storage and reference by both the Boston and local sites. Regarding data transmission, participants and study assessors will complete clinical measures on teleforms. The data from these forms will be securely transported to Boston through a fax machine, which will upload the data from the forms into a restricted access database on a secure network server inside the VA firewall. Hard copies of data files and consent forms will be maintained in secure, locked cabinets at the site in which they are collected.

#### *Assessor Training and Adherence*

A co-investigator, [name] (University of Wyoming) will train the assessors prior to beginning enrollment. Training will include reading and viewing training materials, observation of CAPS administration, and supervised administration of at least three CAPS. [name] has expertise in the conduct of CAPS assessment and has past experience performing training and fidelity monitoring for use of CAPS assessment in clinical trials. Each assessor will be considered trained on CAPS when he or she “matches” [name] on three interviews. To establish matching, [name] will co-rate an interview conducted by the assessor. A match occurs when the assessor and [name] agree on the diagnosis and are within 2 points of severity on all of the symptom clusters (PTSD criteria B, C, D, and E). If the assessor does not match on three interviews after five attempts, [name] will determine whether additional training is necessary or if the assessor needs to be replaced.

All assessments will be audiotaped to ensure that a standardized approach is being used across patients (provided that the participant consents). [name] will review audio recordings of 10% of the assessments, selected randomly. [name] can at his discretion increase the proportion reviewed for difficult patients or assessors needing additional monitoring. Assessors will be provided with feedback about their performance. All recordings will be stored on a restricted-access directory (i.e., only lab personnel with personal usernames expressly granted access may access the directory containing the folder of recordings, and they must log in with their personal username and password to do so) in a locked office maintained at the Boston VA Healthcare System, Jamaica Plain campus. Selected sessions (recordings and interviewer-scored assessments sheets) will be securely transferred to [name] via encrypted email (see attached Data Use Agreement).

Assessors are permitted to do baseline assessments and follow-ups from their home in order to reduce patient and assessor burden. Written consent is obtained at the remote performance sites and any emergency and duty to warn issues are also handled in real time at the respective performance site’s VAs (patients are physically at the respective VAs when interviewed remotely by Boston and research staff are present during the interview time).

#### *Random Assignment*

Veterans will be randomly assigned to PCT or AD-MIL. The Boston site will generate a randomized permuted block scheme to randomly assign patients to blocks by gender and minority status. Block size for gender and minority status will be based on the distribution of these variables at each site. Blocking by gender and minority status will ensure appropriate accrual rates for participants with lower base-rate characteristics. The Boston site will use constrained randomization (i.e., biased coin design; Cook & DeMets, 2008) if unexpected imbalance arises in gender and minority distribution across treatment groups.

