### *Sample Size*

Power calculations were based on a two-sided, two-sample t-test to compare the differences in mean change. Effect sizes were selected based on a trial comparing Acceptance and Commitment Therapy with PCT in veterans with mental health diagnoses, using the SDS (Lang et al., 2016), which showed a large effect size for reduction in disability ( $d \approx .60$ ), a change of 1.2 points. Lang et al.'s (2016) follow-up interval was 3 months. These correspond to 3-month changes of 1.2 points assuming a standard deviation for the change of 2.1 points as per Lang and colleagues. These power calculations inflate the variance to account for clustering of scores (sites by therapists), with an  $ICC = .02$ . To partially offset possible losses to follow-up, we will follow the Benjamini-Hochberg testing procedure, which is less conservative than the Bonferroni rule (Benjamini & Hochberg, 1995). Each hypothesis is powered to compare outcome at 3 months. Analyses up to 6-months post-treatment are exploratory. Testing five hypotheses, each with Type I error of  $1\% = 5\%/5$ , then with 93 participants per arm, a two-sample t-test, comparing the difference between the 3-month changes, has 90% power to detect an absolute difference of .50 or larger assuming an effect size of .56. To have 80% power with 93 participants per arm requires an effect size of .50.

Note: In consultation with RR&D, we recalculated the number of participants to power the original trial at .8 (vs. .9) and this resulted in a new target N of 148 (74 per arm).

**COVID-19 Aim:** We used the AD grant's power framework to estimate the N required to test our hypothesis that AD would lead to better functional changes relative to PCT in COVID-19 stressed veterans with PTSD. We used the same parameters for mean change and the SD for change in Sheehan scores from the grant and a revised differential effect size prediction of .8. We reasoned that we would expect a larger differential effect size for this sub-study because AD can not only help veterans whose existing PTSD symptoms and impairments are exacerbated by COVID-19 stressors but also because AD includes change agents that can help reduce distress and impairment associated with the day to day demands and stressors of living in the time of COVID-19 (mindfulness, loving kindness meditation, letter-writing, behavioral assignments). With these parameters, we need 74 veterans (37 per arm) to power the aim (at a power of 0.90; one-tailed).

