### **ANALYSES**

**Inferential analyses.** The longitudinal and clustered nature of the design produces a multilevel or nested data structure (Raudenbush & Bryk, 2002), with a likelihood of between-subject variability in treatment trajectory over time (e.g. random slopes). In this study, veterans and therapists are nested (clustered) within performance sites. The lower level (level-1) data consists of the repeated measures for each individual at each assessment. Level-1 data is nested within upper level (level-2) person-level variables (e.g., study site).

Using the most up to date statistical software such as SAS 9.4 and R/R Studio, we will explore the change trajectory of endpoints over the course of pre-treatment, during-treatment, and post-treatment time intervals. Specifically, we will use the linear mixed model regression framework to assess the differential treatment effects of endpoint symptom burden over time. We will examine observed measurement scores and specify linear mixed models that best fit the time-change trends (e.g. linear, piecewise). We will test for the presence of random variation, such as between-site cluster effects and between-subject random slopes of treatment effect. We will determine the best fit linear mixed effects model as a combination of most appropriate representation of time and empirically-evidenced random and fixed effects.

The linear mixed effects models will incorporate clinically relevant time-invariant and time-varying predictors and will use Maximum Likelihood Estimation to produce estimates that are unbiased in the presence of random missingness and dropout. They will provide an Intent-To-Treat (ITT) analysis that will incorporate all available data. Per-protocol and “completer” subset analyses will be performed under the same paradigm. Additionally, a subset of subjects whom began therapy during the COVID-19 pandemic will be identified and analyzed separately; they comprise subjects which began therapy following December 31st, 2020. The tenability of the “At-Random” missingness assumption will be assessed and a sensitivity analysis of the results will be conducted to determine robustness of the inferences.

**Aim I:** Randomized controlled trial of AD-E, comparing it to PCT:

**Hypotheses 1 and 2:** Veterans in the AD-E arm will have a steeper downward slope in SDS (primary endpoint). Identical calculations will be performed with the B-IPF and DRRI-2 Post-Deployment Social Support measure.

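### Randomisation is blocked by gender and minority status, but no analysis is committed to using those factors; the likely cost is slightly wide intervals and some lost power, not false positives.

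*Combined protocol and SAP*

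**What the plan says.** Under Random Assignment, a permuted block scheme is used to "randomly assign patients to blocks by gender and minority status". Site comes in through block size: "Block size for gender and minority status will be based on the distribution of these variables at each site". A biased-coin design is held in reserve "if unexpected imbalance arises in gender and minority distribution across treatment groups". No numerical trigger for that switch is given.

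Under ANALYSES (inferential analyses), the fixed part of the model is described only in general terms: "The linear mixed effects models will incorporate clinically relevant time-invariant and time-varying predictors". The predictors are not listed. Site is described as a level of nesting and as something to be tested: "We will test for the presence of random variation, such as between-site cluster effects and between-subject random slopes of treatment effect". The final model is the best-fitting combination of a time representation with whichever random and fixed effects the data support. The primary contrast is the difference between arms in SDS slope, and the other continuous outcomes use the same model structure.

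Two kinds of categorical outcome are compared by chi-square with no stratification or adjustment stated: PTSD caseness (Hypotheses 3-6) and the recovered, improved, unchanged or deteriorated categories (Clinical significance).

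**The concern.** Blocking on a factor makes the arms more alike on it than simple randomisation would. If the factor is related to the outcome, the treatment estimate varies less from trial to trial than an unadjusted model assumes, so the reported standard error is too large. Putting the factor in the model restores the match and recovers the precision.

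Here nothing ties the model to the allocation. Even if gender and minority status were entered at the start, selection by fit could remove them. Design factors are normally kept because they determined allocation, not because they pass a fit test. Site is in a similar position, because its retention depends on a variance test with only four sites, and such a test has little power. Leaving the choice open also lets covariates be settled after outcome data are seen.

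What is at stake is efficiency and prespecification. The Sample Size section has already lowered target power from 0.9 to 0.8, tests each hypothesis at 1%, and states no inflation of N for dropout.

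**Working it through.** **Inputs from the plan.** Sample Size: 148 participants (74 per arm), two-sided 1% test per hypothesis, difference 1.2 points, SD of change 2.1 points. Overview: four sites. **Assumption:** R², the share of between-person variance in observed change explained by the blocking factors. The documents give no value, so I use 0, 2%, 5% and 10%.

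**1. The plan's sample size.** d = 1.2/2.1 = 0.571. Per arm, n = 2(z₀.₉₉₅ + z_power)²/d².
- 80% power: 2 × (2.576 + 0.842)²/0.571² gives 72 (plan: 74).
- 90% power: 2 × (2.576 + 1.282)²/0.571² gives 92 (plan, before the reduction: 93).

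Both agree closely, with no inflation for clustering. The power figures below start from this same base.

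**2. Size of the mismatch for a comparison of change.** With the factors balanced by blocking and left out of the model:
- ratio of reported to true standard error = 1/√(1−R²)
- equivalent patients, by interval width = 148/(1−R²) − 148
- actual type I error at nominal 0.01 = 2[1 − Φ(2.576/√(1−R²))]

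| Assumed R² | SE too large by | Equivalent patients | Actual type I error | Power without factors | Power with factors |
|---|---|---|---|---|---|
| 0 | 0% | 0 | 0.0100 | 81.6% | 81.6% |
| 2% | 1.0% | 3.0 | 0.0093 | 81.8% | 82.5% |
| 5% | 2.6% | 7.8 | 0.0082 | 82.2% | 83.9% |
| 10% | 5.4% | 16.4 | 0.0066 | 82.9% | 86.2% |

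Power is by normal approximation at 74 per arm and d = 0.571. The gain from adjusting is 0, 0.7, 1.7 or 3.3 percentage points.

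**3. Simulation check of step 2.** N = 148, blocks of 4 within site × gender × minority strata, R² = 10%. The mean reported SE without the factors was 0.164, against an actual SE of 0.158-0.159; with the factors the reported SE was 0.156. Type I error at nominal 0.01 was 0.0076 without and 0.0101 with the factors. Power was 81.7% and 85.2%.

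**4. The primary contrast is a slope.** A factor that shifts only the level of SDS drops out of a within-person slope. In a simulation with N = 148, four equally spaced visits, the same blocking, and random intercepts and slopes, the mean reported SE of treatment-by-time (arbitrary units) was:

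| Factors affect | No factors | Main effects only | Main effects and time interactions |
|---|---|---|---|
| Level only | 0.0984 | 0.0984 | not needed |
| Level and slope | 0.1032 | 0.1032 | 0.0966 |

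A further blocked run at N = 148 compared reported with actual SE when the factors predict change: 0.102 reported without the factors, 0.098 actual, 0.099 reported with factor-by-time terms. With level-only effects there was no difference. The slope effects in these runs were chosen to show the mechanism and do not estimate its size in this trial.

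For the primary endpoint, then, the table in step 2 applies only if R² is read as variance in change, and only time interactions recover the precision.

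**The case against.** The strongest reply is that the plan under-specifies the model rather than excluding the factors. Gender and minority status do not change over time and could be among the predictors it promises. This stands for the mixed model: a reader might infer that the model omits them, but no text says so. It does not answer the complaint that selection by fit can drop them, and it does not reach the chi-square tests, for which no stratification or adjustment is stated.

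Second, the effect is mild and conservative, and may be zero for the primary slope. This also stands. At every assumed R², planned power stays above 80% without adjustment on the plan's own inputs, and the required N does not rise.

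Third, a reader might infer that randomisation was stratified by site. The text ties site only to block size, and ANALYSES already treats site as nesting. The case for keeping site therefore rests on not conditioning on a weak variance test, rather than on a stated stratum.

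Fourth, a reader might infer that triggering the biased coin would invalidate an unadjusted analysis. The documents make it a contingency, blocking already makes allocation depend on these factors, and nothing here shows added harm. It is a reason to fix the covariate set in advance, no more.

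**Conclusion.** The point holds as a gap in prespecification with a modest cost. Allocation is constrained by gender and minority status, and no analysis is committed to using them. If they explain 2% to 10% of between-person variance in change, leaving them out makes standard errors about 1.0% to 5.4% too large and costs about 0.7 to 3.3 points of power. If they predict only the level of SDS, the cost for the primary slope contrast is nil. The share explained is an assumption throughout, so confidence is high about the omission and low about its size.

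Type I error stays at or below nominal, so this is no ground for doubting a positive result. Nor should the calculation be applied to the share of SDS variance itself, as a reader might be tempted to do: a large share in level can leave the slope standard error unchanged.

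**What to change.** Amend ANALYSES to state:
- Every mixed model includes gender and minority status as fixed effects, each with its interaction with time. They are kept regardless of fit and whether or not the biased coin is used.
- Site (four levels) is kept in the same way, not conditional on a test of between-site variance.
- PTSD caseness and the clinical-significance categories are compared with a stratified test (for example Cochran-Mantel-Haenszel, in its general form for the four categories) or a covariate-adjusted one, using the same factors. The choice is named in advance.

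Main effects alone would not be enough, for the reason shown in step 4 of the working.

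**Cost.** A few sentences and no new data. Gender (1), minority status (1) and site (3) use five degrees of freedom, and their interactions with a single linear time term use five more, about ten in all. A piecewise time trend would use more. If the factors turn out not to be prognostic, the loss is negligible: in the simulation with R² = 0, adding gender and minority status moved the mean reported SE from 0.1640 to 0.1642.

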#### *Treatment Arms*

AD-MIL is a modification and extension of Adaptive Disclosure (AD; [name] et al., 2015) which utilizes existing change agents in AD to address self-blame and guilt associated with trauma in several ways. In-session dialogue about traumatic events helps veterans understand and make sense out of their various shame- and guilt-related concerns. In addition, AD-MIL extends these change agents by also including session content focused on building in skills training and behavioral contracting to improve functioning, and targeting trauma-related psychological and behavioral obstacles to positive and potentially habituative engagements in occupational, relationship, and family roles. Homework assignments to be completed between therapy sessions are generated collaboratively in session. For MI, homework activities may entail increased reparative time spent volunteering or with other veterans, family, and friends, and engaging in meaningful activities and/or spiritual practices, to counteract self- or other-condemnation. For TL, homework may entail restoring attachments and engaging in positive and wellness-promoting behaviors. For life-threat traumas, homework may include engaging in valued activities and relationships to counteract fear-driven avoidance. The AD-MIL manual adheres to consensus guidelines for replicable and functionally viable treatment manuals, including: (1) specific and operationalized procedures for goal-setting, target-selection, and monitoring process and outcome; (2) detailed session-by-

session instructions and content with examples and vignettes; and (3) supervisor instructions for bolstering competence and maintaining adherence (Carroll & Nuro, 2002).

PCT is a manualized evidenced-based PTSD treatment (Frost et al., 2014) used in several large-scale PTSD trials (e.g., Schnurr et al., 2007). It incorporates the essential therapeutic elements common to different types of psychotherapies, including supportive empathic listening and unconditional positive regard. The therapist plays an active role but does not impart any systematic training. The focus is to create an understanding of how the symptoms of PTSD are related to day-to-day difficulties and to help patients develop new, more adaptive responses to these stressors with a problem-focused and problem-solving approach. PCT includes weekly homework assignments. These include reading psychoeducational handouts and self-monitoring problems and stressors in a daily diary, which are then problem-solved in session. In prior trials, PCT showed equivalent change to active therapies at the last follow-up. The VA offers PCT as an evidence-based therapy for PTSD. So, this design element represents a conservative test of the superiority of AD-MIL.

Participants in both treatment arms will receive 12 weekly 90-minute sessions of individual psychotherapy.

#### *Treatment Training, Supervision, and Fidelity Monitoring*

Therapists with Ph.D.s in clinical or counseling psychology and VA internship experiences treating veterans with PTSD will be trained to deliver AD-MIL or PCT (not both).

Training and supervision of AD-MIL and PCT trial cases will be provided by Drs. [name] and [name]. [name] developed AD for the Marine Corps trial and has spearheaded the extension of AD principles in the development of AD-MIL. [name] has extensive expertise in the conduct of PCT. Training will involve a review of the respective manuals and supporting materials, intensive supervision of trial cases, and weekly group and one-on-one phone supervision with [name] for AD-MIL and [name] for PCT). Drs. [name] and [name] will review audio recording of treatment sessions (all treatment session will be audiotaped) as needed to facilitate their supervisory roles. Selected sessions will be securely transferred to an approved and secure drive within the VA firewall to Drs. [name] and [name].

Treatment fidelity monitoring will be conducted by Drs. [name] and [name]. [name] was instrumental in the development of AD for the Marine Corps trial and has served as a consultant in the extension of AD principles in the development of AD-MIL. [name] has extensive expertise in the conduct of PCT. Fidelity monitoring will be executed via the following procedure: 100% of a patient's first two sessions will be selected for review, 50% of next two, 20% of next five and 10% thereafter. After ten subjects, the therapist will discuss with the site RA which sessions to send for review to total 10% of caseload. Selected sessions will be securely transferred to an approved and secure drive within the VA firewall to [name]. Selected sessions will be securely transferred to [name] via encrypted email (see attached Data Use Agreement).

#### *Data Safety Monitoring Board (DSMB), Adverse Events (AE), Unanticipated Problems Involving Risk (UPR), and Protocol Deviations*

**Data Safety Monitoring Board (DSMB):** A DSMB has been created for the study, including Drs. [name], [name], and [name] at the VA Boston Healthcare System. The DSMB is tasked with independently ensuring the safety of study participants and scientific goals. The DSMB will review the initial protocol and any proposed amendments, meet and complete reports bi-yearly, perform expedited monitoring of all serious adverse events, perform ongoing monitoring of drop-outs and non-serious adverse events, determine whether study procedures should be changed or the study should be halted for reasons related to the safety of study subjects, and perform periodic review of the completeness and validity of data to be used for analysis of safety and efficacy. The DSMB will also ensure subject privacy and research data confidentiality. A statistical

penalty will not be assessed for the ongoing unblended review of safety by the DSMB. Unblinded data will not be released to investigators unless necessary for safety reasons. Suspected information security and privacy incidents will be reported within one hour to the Information Security and Privacy Officers and Research Administration.

**Adverse Event (AE):** An adverse event (AE) is any untoward physical or psychological occurrence directly or indirectly affecting a human subject participating in research.

Adverse Event is a broad term covering physical, psychological, social, legal or economic occurrence directly or indirectly affecting a human subject participating in research. An AE can be any unfavorable or unintended event including abnormal laboratory finding, symptom or disease associated with the research or the use of a medical investigational test article (includes drug, biologic, or device). An AE may or may not have a causal relationship with the research, or any risk associated with the research or the research intervention, or the assessment. Adverse events involve participants only.

Negative events that are **unanticipated and unrelated** (by reasonable judgment) will be logged and tracked over the course of the study and reported in a summary of their occurrence at DSMB bi-yearly meetings, as well as for continuing reviews and at end of study. Examples might include medical problems, legal problems, homelessness, or traumatic events.

The therapist will query about adverse events (AEs) at every session by asking about any notable events since the last visit. These will be reviewed in a timely manner with the supervisor.

**Serious Adverse Event (SAE):** A SAE occurring in a patient or subject enrolled in a research study is serious if it results in any of the following outcomes: death, a life-threatening adverse drug experience, inpatient hospitalization or prolongation of existing hospitalization, a persistent or significant disability/incapacity, or is a congenital anomaly/birth defect. This will be reported to the IRB within 5 business days, as stated in reporting requirements. The only exception is death, which requires immediate reporting.

**Unanticipated Problems Involving Risk (UPR):** Defined as being (1) unexpected given the research procedures and characteristics of the population, (2) related (or possibly related) to participation in the research and (3) indicative that the research may place the subject or others at a greater risk of harm than was previously known. UPRs require notifying the IRB immediately.

Examples of possible UPRs for psychotherapeutic interventions:

1. Psychosis or mania
2. New onset or clinically significant exacerbation of a psychiatric disorder
3. Suicide and suicide attempts

An incident, experience, or outcome that meets UPR criteria generally will warrant consideration of substantive changes in the research protocol or informed consent process/document or other corrective actions in order to protect the safety, welfare, or rights of subjects or others. Examples of corrective actions or substantive changes that might need to be considered in response to an unanticipated problem include:

- \* modification of inclusion or exclusion criteria to mitigate the newly identified risks;
- \* implementation of additional procedures for monitoring subjects;
- \* suspension of enrollment of new subjects;

- \* suspension of research procedures in currently enrolled subjects;
- \* modification of informed consent documents to include a description of newly recognized risks; and
- \* provision of additional information about newly recognized risks to previously enrolled subjects.

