
### Procedures

**NOTE - PANDEMIC-RELATED CHANGES:** As of August 2020, the entire AD-MIL study is being conducted virtually due to the COVID-19 pandemic. We have provided more information on how we are adapting to these times.

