#### *Follow-Up Assessments*

Follow-up assessments will be completed 3 months, 6 months, and 9 months after the first treatment session, or, if no treatment sessions were attended or a participant terminated therapy early, 3 months, 6 months and 9 months after the baseline assessment. As part of these follow-up assessments, all participants will complete CAPS-5 assessments by phone with an IE. In most instances, these calls will occur while the participant is in person at their local VA (i.e., Minneapolis, San Diego, San Francisco, or Central Texas). In cases where a participant is unable to attend a follow-up assessment at their local VA in person, we will offer participants the opportunity to complete the CAPS-5 assessment by phone from their home or another non-VA location. In instances where the participant is not at their local VA, IEs will conduct a thorough risk assessment during the call, and follow thoroughly defined procedures for risk management and safety planning when indicated (see “Follow-up Risk Assessment Phone Script” attached).

**COVID-19 aim:** Participants randomized between 12/31/2020 and 5/31/2021 will complete follow-up assessments 3 months and 6 months after the first treatment session, or, if no treatment sessions were attended or a participant terminated therapy early, 3 months and 6 months after the baseline assessment. Participants randomized between 6/1/2020 and 8/31/2021 will complete a follow-up assessment 3 months after the first treatment session, or, if no treatment sessions were attended or a participant terminated therapy early, 3 months after the baseline assessment.

**COVID-19 Changes:** All communication with participants is being conducted either via a HIPAA-compliant videoconferencing platform or over the phone.

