## **Reporting Requirements:**

**UPR:** Immediately notify IRB

**SAE:** Report to IRB within 5 business days

**AE that is unanticipated and unrelated:** Track in AE Log (summary will be reported quarterly to DSMB and as needed)

**All other AEs:** Report to IRB within 10 business days

To report to the IRB, an AE form, SAE form, and/or UPR form will be completed, the site PI's signature will be obtained, and the form will be submitted to the local IRB. The form (with encryption) will be emailed to the Study Coordinator. The Coordinator will forward each completed AE/SAE/UPR form to Data Safety Monitoring Board as soon as possible and will maintain a record of all AEs/SAEs/UPRs (see AE Log) to report to the Boston IRB in summary or table form at the time of annual Continuing Review. In the case that a Boston IE learns of an AE/SAE/UPR during the course of a telephone contact, the IE will initiate the AE/SAE/UPR Form and email (with encryption) to the local PI at the site where the participant was recruited (i.e., [name]: Minneapolis, [name]: San Diego, [name]: San Francisco, or [name]: Central Texas) for signature and submission to the local IRB (i.e., the site at which the participant was seen). The Study Coordinator will notify RR&D of any UPR, AE, or SAE promptly via encrypted email.

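### The only scheduled general adverse-event question is asked at therapy sessions, so capture after the last session attended is incidental and depends on staying in therapy

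*Combined protocol and SAP*

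**What the plan says.** The section on the DSMB and adverse events assigns the query to the therapist: "The therapist will query about adverse events (AEs) at every session by asking about any notable events since the last visit". Under Treatment Arms, "Participants in both treatment arms will receive 12 weekly 90-minute sessions of individual psychotherapy".

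Follow-up runs well past therapy. Under Follow-Up Assessments, "Follow-up assessments will be completed 3 months, 6 months, and 9 months after the first treatment session", and non-starters and early terminators stay on a schedule of their own: "if no treatment sessions were attended or a participant terminated therapy early, 3 months, 6 months and 9 months after the baseline assessment". Participants randomized late, under the COVID-19 aim, have shortened schedules that end at 6 or 3 months.

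The stated content of these visits is clinical assessment: "As part of these follow-up assessments, all participants will complete CAPS-5 assessments by phone with an IE". There is also a safety element: "In instances where the participant is not at their local VA, IEs will conduct a thorough risk assessment during the call". The Procedures section adds "As of August 2020, the entire AD-MIL study is being conducted virtually due to the COVID-19 pandemic", so from then on the off-site condition would apply to most calls. No general AE question is listed for these visits.

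Outside sessions, Reporting Requirements describes what happens to the paperwork "In the case that a Boston IE learns of an AE/SAE/UPR during the course of a telephone contact". It does not tell the evaluator (IE) to ask, and it names only Boston evaluators, although the consent and screening section says that staff at all sites may serve as IEs.

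**The concern.** The protocol's AE definition is broad. It takes in physical and psychological events and also social, legal and economic ones, and a hospital admission counts as serious. A definition that wide needs someone to ask. As written, the asking stops when the veteran attends a last session, whether that is session 12, session 4 or none.

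Two things are at stake. First, events in the months after therapy, and in veterans who left early, will be under-recorded. Secondly, the number of events recorded depends on how long people stay in therapy. If one treatment loses more veterans than the other, its AE count falls for that reason alone, and anyone looking at counts by arm would be misled.

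**Working it through.** The plan states no AE rate and no ascertainment figure, so there is no figure of its own to reproduce. The check is on the schedule.

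**Inputs**
- 12 weekly sessions (Treatment Arms). With the first at week 0, the twelfth falls at week 11.
- Follow-up of 9, 6 or 3 months (Follow-Up Assessments, including the COVID-19 schedules), taken as W = 39, 26 or 13 weeks.
- The query looks back to the previous visit. A veteran whose last session is number k is therefore covered for k − 1 weeks if sessions are weekly.
- 74 per arm (Sample Size), used only in the illustration.

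Non-starters and early terminators are timed from baseline rather than from the first session. The small difference is ignored here.

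**Step 1: share of follow-up time within the session query.** Covered share = (k − 1)/W.

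| Last session attended | 9-month schedule | 6-month schedule | 3-month schedule |
|---|---|---|---|
| 12th | 11/39 = 28% | 11/26 = 42% | 11/13 = 85% |
| 4th | 3/39 = 8% | 3/26 = 12% | 3/13 = 23% |
| none | 0% | 0% | 0% |

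The uncovered share for a completer is therefore 72%, 58% or 15%. For a veteran who stops after session 4 it is 92%, 88% or 77%. For a non-starter it is 100%. These are shares of time, not of events.

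**Step 2: effect of unequal stopping on counts by arm.** The documents give no drop-out or AE rate, so these are assumptions: the same constant weekly AE rate in both arms, drop-outs stop for good after session 4, everyone else completes, and only session-captured events are counted. With drop-out proportion d,

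query-weeks per arm = 74 × [(1 − d) × 11 + d × 3].

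- d = 20%: 74 × 9.4 = 696
- d = 30%: 74 × 8.6 = 636
- d = 40%: 74 × 7.8 = 577

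Ratio of captured AEs against an arm with 20% drop-out: 696/696 = 1.00, 636/696 = 0.91, 577/696 = 0.83. The arm size cancels. Events that reach the log by other routes would pull the ratio back towards 1.

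**Step 3: missed sessions.** A veteran who misses session 5 and returns for session 6 is asked then about the whole interval. An occasional missed session therefore loses nothing; only permanent stopping does.

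**Step 4: what the other follow-up contents cover.** The off-site risk assessment addresses acute danger. The CAPS-5, PCL-5, PHQ-9 and DSI-SS address PTSD, depression and suicidal ideation. None of these asks about a hospital admission, a medical problem, an arrest or loss of housing. The weekly PCL-5, which the Measures section says is partly meant to pick up adverse outcomes, is also tied to therapy.

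**The case against.** A reader might infer that drop-outs, and everyone after treatment, get no scheduled safety question at all. The documents do not support that. Non-starters and early terminators remain in follow-up, off-site calls carry a mandatory risk assessment, and conduct has been virtual since August 2020. The symptom and suicidality scales are analysed as slopes over time and are not on the baseline-only list, so collecting them at follow-up is a fair inference, although there is no visit-by-visit table. Clinically important psychiatric worsening would probably surface through these routes. This part of the objection stands, and it narrows the gap to AEs of other kinds.

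A reader might also infer that a planned arm comparison of AEs is biased. The ANALYSES section contains no such comparison, and the DSMB tracks drop-out alongside AEs, so an imbalance in stopping would not go unseen. This also stands: the bias is conditional on counts being reviewed by arm. Such a review is plausible, however. The DSMB section describes a continuing safety review, withholds unblinded data from investigators, lets the board decide whether to halt, and mentions a safety analysis. Seeing drop-out next to AE counts warns the board but does not recover the missing events.

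Finally, the duty to report AEs is not confined to therapists or evaluators, and the risk-assessment phone script and AE forms are attachments not available here. They may contain a general question. If so, the protocol text should say so. A duty to report what one learns is still not an instruction to ask.

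**Conclusion.** The point holds in a limited form. The only general AE query that the plan schedules is the therapist's, at sessions. After the last session attended, capture of events such as hospital admission or medical, legal and social problems is incidental. For a completer this leaves about 72% of the 9-month schedule, 58% of the 6-month schedule and 15% of the 3-month schedule without a general AE query; for a non-starter it leaves 100%. These figures rest on weekly attendance and on months counted as 13-week quarters. The 72% should not be quoted for the shortened COVID-19 schedules, nor read as the share of events missed.

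If AE counts are reviewed by arm and permanent stopping differs, the arm with more stopping will look safer than it is. The 0.91 to 0.83 range shows the possible size under assumed drop-out and a constant, equal event rate; it is not a forecast. This is an inexpensive improvement to safety ascertainment, not a flaw in the efficacy design.

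**What to change.** Add to Follow-Up Assessments that site staff other than the blinded IE ask every participant the same standard AE question, covering the time since the last contact. Ask it at each scheduled assessment (3, 6 and 9 months, or the shortened COVID-19 schedule), whether or not therapy was attended. Keeping it away from the IE avoids answers that might reveal the arm.

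Report AEs to the DSMB by arm, by observation period (in therapy versus follow-up) and per person-time. The split by period matters because recall over about three months is likely to be less complete than recall over one week, so the two periods should not be pooled without comment.

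For everyone who completes the scheduled assessments, this brings the whole of follow-up under a general AE query and removes the dependence on staying in therapy. Veterans lost to follow-up altogether remain unasked, and the person-time denominator makes that visible.

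The contacts, forms and reporting route already exist. The cost is one question per visit and a few more forms to process.
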